6.5.1.2 Data Submission

Once required testing has been performed, complete and submit the appropriate forms to St. Jude Medical. Refer to Table 5: Study Procedures and Data Collection

Upload the pre-MRI scan device session records through the EDC study portal. It is recommended that the following device printouts and measurements be maintained at the site.

- FastPath Summary
- Test Results with Freezes, Include Battery & Leads
- Wrap-up Overview with full parameters
- Device MRI summary report

6.5.2 Situations where the subject does not meet enrollment criteria

If a subject does not meet all inclusion criteria or meets any of the exclusion criteria, the subject cannot participate in the study and cannot be enrolled.

In case the subject was already consented to participate in the study, but did not meet inclusion/exclusion criteria, the following actions will be taken (Table 7). The EC/IRB and CA/FDA should be notified of deviations according to each respective entity's guidelines.

Clinical Investigational Plan

Table 7: Actions for Inclusion/Exclusion Criteria Issues that Occur Post Consent

Issues where patient was consented, but did not meet inclusion/exclusion criteria	Action
If the MRI Scan Visit has not yet taken place and the MRI Settings was not programmed	
 • Document consenting information (name of the study, date of consent and inclusion/exclusion) in the subject’s medical and/or study records • Submit the Baseline CRF and Screening Failure CRF. The subject is a screen failure.
If the MRI Pre-Scan Visit has taken place, the MRI Settings was NOT programmed and the study MRI scan was NOT completed (e.g. Subject changed their mind about undergoing MRI scan, etc.)	
 • Document enrollment (name of the study, date of consent and inclusion/exclusion), MRI Scan Visit and study MRI scan information in the subject’s medical and/or study records • Complete the Baseline Form • Complete the Pre-MRI Scan Form • Note that the subject did not have the MRI Settings programmed on the pre-MRI CRF. • Submit the Screening Failure CRF. The subject is a screen failure.
If the MRI Pre-Scan Visit has taken place, the MRI Settings WERE programmed but the study MRI scan was NOT completed (e.g. Subject changed their mind about undergoing MRI scan, etc.)	
 • Document enrollment (name of the study, date of consent and inclusion/exclusion), MRI Scan Visit and study MRI scan information in the subject’s medical and/or study records • Complete the Baseline Form • Complete the Pre-MRI Scan Form • Complete deviation for inclusion/exclusion criteria not met • Complete the Withdrawal CRF. The patient is withdrawn.
If the MRI Pre-Scan Visit has taken place, the MRI Settings were programmed AND the study MRI scan has been performed	
 • Document enrollment (name of the study, date of consent and inclusion/exclusion), MRI Scan Visit and study MRI scan information in the subject’s medical and/or study records • Complete the Baseline Form • Complete the Pre-MRI Scan Form and MRI Scan Form • Complete deviation for inclusion/exclusion not met • Continue to follow the subject through the 1 Month Post MRI Scan Visit.

Clinical Investigational Plan

6.5.2.1 The MRI Scan

After confirmation by the electrophysiologist or device specialist that all pre-MRI system checks (mentioned above) have been met, subjects will have their MRI scan completed by a radiology staff member. Note: If the patient does not pass the Pre-MRI scan System Check specified above, then the patient should not undergo an MRI scan. The patient can be rescheduled to come back to repeat the Pre-MRI scan System Check testing within the visit window.

Protocol required MRI scan sequences for each subject undergoing an MRI scan are described in detail in Appendix E. It is recommended that the MRI scan be set up on the MRI scanner in advance of the first subject scheduled for a study scan to ensure the scan has been appropriately programmed, and to provide adequate time to address any questions or issues that may arise.

Subjects will undergo two different scans for the study, both of which will expose the ICD to extreme scanning conditions: (1) a thoracic scan that is RF intensive, and (2) a head scan that is gradient intensive. The thoracic scan should be set up to last about 6 minutes and 15 seconds, and the head scan should be set to get as close as possible to 5 minutes without being under 5 minutes. The thoracic scan will need to be repeated 4 times to ensure the subject is scanned approximately 25 minutes. Further details about the set-up, programming and ways to adjust the parameters for MRI scans can be found in Appendix E.

The subject may be in the bore or near the vicinity of the magnet for approximately 60 minutes. The actual amount of time the subject will be scanned is about 30 minutes: 25 minutes for the thoracic scan, and 5 minutes for the head scan.

These two MRI scans are not intended to be diagnostic in nature and therefore the administration of contrast fluids or sedation, or the application of water and fat saturation techniques are not permitted.

Consult the “MRI Ready Systems Manual. MRI Procedure Information for the St. Jude Medical™ MR Conditional System” for guidelines and `precautions related to conducting an MRI scan with the implanted study ICD system.

NOTE: The non-clinical study MRI scan in this study is being performed to demonstrate safety and MRI compatibility of the Durata or Optisure lead and Ellipse ICD for an MRI scan, and is not meant to be diagnostic in nature. The MRI scan will not be read by the radiologist.

If subject movement causes distortion on the MRI, do not repeat the MRI scan.

Clinical Investigational Plan

Cardiac Monitoring

During the entire MRI scan, the subject's cardiac function must be monitored using pulse oximetry and an ECG by an MRI Ready IDE study trained electrophysiologist, cardiologist, or Advanced Cardiac Life Support (ACLS) trained personnel capable of delivering external cardiac pacing defibrillation and advanced cardiac life support. Verbal communication with the subject must also take place to assess and/or confirm any clinically significant changes noted in the subject's oxygen saturation or heart rate, as well as any clinically significant complaints not obvious with pulse oximetry. Record these changes and complaints during the MRI scan.

ACLS procedures must be in place to address situations where a life threatening arrhythmia and/or hemodynamic collapse occurs. The programmer must be used outside the American College of Radiology (ACR) defined Zone 4 magnet room. If the subject's hemodynamic function is compromised during the MRI scan, discontinue the MRI procedure and take proper measures to restore the subject's hemodynamic function.

Life-threatening Ventricular Arrhythmia and Asystole Assessment

Monitoring of spontaneous ventricular arrhythmias and asystole must be conducted via an ECG and pulse oximetry during the MRI scans. Any sustained ventricular arrhythmias or asystole (see definition below) must be documented on an Adverse Event form. Non-sustained ventricular tachycardias (NSVT) or premature ventricular contractions (PVCs) do not need to be reported as an adverse event. However, if an arrhythmia reproducibly occurs (occurring more than once during the study scan) while the subject is actively being scanned, report the event on an Adverse Event form.

Definitions:

- *Sustained Ventricular Arrhythmia:* Heart Rate >150bpm for > 30 seconds with depolarization originating in the ventricles
- *Asystole:* A standstill > 6 seconds in electrical activity of the heart (i.e., no heart rate for 6 seconds or more)

Handling of Subjects Unable to Tolerate an MR Scan

In cases where the scan cannot be tolerated by the subject, remove the subject from the scanner. Assess the subject for possible adverse events, and treat the subject's reported symptoms according to your institution's standard of practice. Document the reason for the intolerance. At a minimum, information related to the sequence used to perform the scan, the length of time the subject was scanned, and the whole body SAR level reached should be collected and submitted to St. Jude Medical. A repeat scan is not required to be completed. The subject is not withdrawn from the

Clinical Investigational Plan

study. The subject should be scheduled to return for their 1 month post MRI scan visit.

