- In-clinic bipolar sensing amplitude. Either the incremental or the automatic (in-clinic, programmer based) method may be used to obtain the sensing threshold. **Note: If the ventricular sensing is not measurable (patient has underlying rhythm < 30bpm) and the sensing amplitude is < 4mV, then the patient does not meet inclusion criteria.**
- In-clinic bipolar pacing and high voltage lead impedance

NOTE: RV capture thresholds are not required to be obtained if a high ventricular rate is present (e.g. 110bpm). If available, sites should use the automatically obtained pacing capture threshold from the most recent archival data as a substitute for the in clinic capture threshold. RV sensing measurements are not required if the subject's intrinsic rate has been established to be ≤ 30 beats per minute.

If the device testing results do not meet the MRI conditions for scanning per the MRI Procedure manual (also see below), or the patient's sensing threshold is not measurable or the sensing threshold is less than 4mV, the physician may choose to reschedule the subject to return for re-testing. The subject's 1 Month Post MRI Scan Visit will need to be rescheduled to correspond with the MRI Scan Visit where the MRI scan was completed.

Review the MRI checklist on the programmer. Verify the following conditions before saving the MRI Setting.

- Bipolar capture thresholds are stable at $\leq [contact]$ ms
- Bipolar pacing lead impedance is within range, i.e. ≥ 200 and ≤ 2000 ohms
- HVLI is within range, i.e. ≥ 20 and ≤ 200 ohms
- No additional hardware (adaptors, extenders, or abandoned leads)

Save the MRI Setting after the MRI Checklist has been reviewed, using the parameters listed in Table 6: MRI Parameters. Perform all other applicable tests and procedures.

Clinical Investigational Plan

Table 6: MRI Parameters

Parameters	Selectable Options	Nominal Values
MRI Mode*	VOO Pacing Off	Pacing off
MRI Base Rate	30-100 bpm, in steps of 5 bpm	n/a
MRI RV Pulse Configuration	Bipolar	n/a
MRI RV Pulse Amplitude	5.0 V, 7.5 V	n/a
MRI RV Pulse Width	1.0 msec	n/a
Tachy settings	Disabled	Disabled

***Note:** When MRI Settings are enabled, sensing is disabled. Determine whether or not the subject requires pacing support during the MRI scan. When pacing support is needed, set the MRI Mode to the asynchronous pacing mode (VOO). When pacing support is not needed, set the MRI Mode to Pacing Off.

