Some subjects may be susceptible to cardiac arrhythmia induced by competitive pacing when an asynchronous MRI Mode is selected. For these subjects, it is important to select an appropriate MRI pacing rate to avoid competitive pacing and then minimize the duration of the asynchronous pacing operation.

In MR Conditional ICDs, tachytherapy is disabled when the MRI settings are programmed.

After the electrical measurements for the RV lead have been taken, capacitor maintenance has been performed, the MRI Checklist (on the programmer) verified and the MRI Setting saved, activate the MRI parameters.

Setting up Pulse Oximetry and ECG

Set up pulse oximetry and an ECG per standard of care.

Place the oximetry clip on the subject’s finger or other any other appendage that results in valid pulse oximetry readings. Position MRI compatible surface electrodes on the subject to ensure the subject’s heart rate can be continuously monitored during the scan. During the MRI scan, periodically record heart rate, and blood oxygen saturation levels. Visually examine the ECG during the MRI scan. Note any abnormalities observed in the cardiac rhythm (Refer to Life-threatening Ventricular Arrhythmia and Asystole Assessment below). After the MRI scan, remove the subject from the MRI field.

Definition of enrollment:

The patient will be considered enrolled in the study after the main study consent is signed by the patient, it has been verified during the MRI visit that the subject meets

Clinical Investigational Plan

all of the inclusion and none of the exclusion criteria, and the MRI Settings have been programmed.

The following documentation activities should be performed after the subject has been consented.

- Record enrollment information (name of the study, date of consent and inclusion/exclusion information) in the subject's medical and/or study records
- Complete and submit the Baseline and Pre-MRI CRFs in a timely manner (recommended within 5 days)
- Notification of enrollment to the sponsor will take place when the sponsor receives the Pre-MRI Scan CRF Form indicating that the MRI Settings has been enabled.

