6.5.2.2 Post-Scan Testing

Device Assessment and Programming

Following the MRI Scan, remove the subject from the MRI bore. Interrogate the ICD. Disable the MRI Settings. **Note: MRI settings must be disabled to ensure that tachyarrhythmia therapy is turned back on.** Obtain the following for the Durata or Optisure lead:

- In-clinic bipolar capture threshold at a pulse width of 0.5 ms. Either the manual decrement or automatic (in-clinic, programmer-based) method may be used to obtain the capture threshold.
- In-clinic bipolar sensing amplitude. Either the incremental or the automatic (in-clinic, programmer based) method may be used to obtain the sensing threshold.
- In clinic bipolar lead impedance
- In-clinic HVLI impedance

NOTE: RV capture thresholds are not required to be obtained if a high ventricular rate is present. If available, sites should use the automatically obtained pacing capture threshold from the most recent archival data as a substitute for the in clinic capture threshold. RV sensing measurements are not required if the subject's intrinsic rate is established to be ≤ 30 beats per minute.

Reporting of MRI Scan-Related Adverse Device Effects

An ADE or SADE related to the following should be reported as soon as possible, but no later than 10 working days, to St. Jude Medical: clotting, pulmonary embolism, or heating of the device pocket during the MRI scan. These events are likely to be associated with symptoms occurring during or immediately following the MRI scan and may manifest as chest pain, shortness of breath, or changes in vital signs during or immediately following the MRI scan.

To ensure all ADEs or SADEs related to or caused by the MRI scan are appropriately captured, before starting the scan, verbally instruct the subject to report symptoms of chest pain, shortness of breath or pocket discomfort that he/she experiences while being scanned or immediately after exiting the scanner. Note changes in vital signs such as changes in heart rate, room air blood oxygen saturation, and/or respiration rate that occur during the MRI scan that may suggest an ADE or SADE has occurred due to clotting, pulmonary embolus or related to lead tip or device pocket heating.

Clinical Investigational Plan

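### Required ECG, oximetry and trained attendance are tied to the MRI scan, while sensing and tachytherapy stay off from MRI Settings activation until the Settings are disabled after it

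*Combined protocol and SAP*

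**What the plan says.** **Device state.** The note to Table 6 (CIP 6.5.1.1) says "When MRI Settings are enabled, sensing is disabled". The same section adds: "In MR Conditional ICDs, tachytherapy is disabled when the MRI settings are programmed". Activation closes the pre-scan device work: with measurements and capacitor maintenance done, "the MRI Checklist (on the programmer) verified and the MRI Setting saved, activate the MRI parameters". Restoration comes in 6.5.2.2, after the subject is out of the bore and the ICD has been interrogated: "MRI settings must be disabled to ensure that tachyarrhythmia therapy is turned back on". Under 6.5.2.1, "The programmer must be used outside the American College of Radiology (ACR) defined Zone 4 magnet room".

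**Monitoring.** Section 6.5.2.1 sets the main duty: "During the entire MRI scan, the subject's cardiac function must be monitored using pulse oximetry and an ECG". It names who may do this: a study-trained electrophysiologist or cardiologist, or ACLS-trained personnel able to pace and defibrillate externally. Section 6.5.1.1 describes ECG and oximetry set-up after the activation step, with electrodes placed so that the subject's "heart rate can be continuously monitored during the scan". Section 3.7 and Tables 1, 2 and 5 also place monitoring or attendance during the scan.

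**Standing provision.** Section 6.5.2.1 also requires, with no time limit, that "ACLS procedures must be in place to address situations where a life threatening arrhythmia and/or hemodynamic collapse occurs". Table 2 has a similar line.

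**Scan not done.** Table 7 has a row for Settings programmed with no completed scan. It lists documentation, forms, a deviation and withdrawal.

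**The concern.** The period with therapy off and the period with required monitoring have different start and end points. With sensing off, the device neither sees nor treats a ventricular arrhythmia, so surface ECG and a person able to defibrillate stand in for it. As written, that substitute is required only for the scan, and therapy cannot come back until the subject is where the programmer may be used.

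The CIP recognises the hazard. Table 2 lists ventricular arrhythmia induced by asynchronous pacing in MRI mode while the subject is ambulatory, and 4.4.3 plans to count subjects whose reprogramming is delayed. At stake is the safety of ICD patients who have no direct benefit from taking part (section 3.0). The primary endpoints and their tests are not affected.

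**Working it through.** The check is a comparison of texts. The only relevant figures are the scan times.

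1. **The plan's own times (6.5.2.1).** Thoracic: 4 × 6 min 15 s = 25 min. Head: 5 min. Total: 25 + 5 = 30 min, which reproduces the stated figure of about 30 minutes. Time in or near the magnet is about 60 min, so about 60 − 30 = 30 min is spent there without scanning.

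2. **How much of that is uncovered.** Section 8.1.6, which defines scan-related complications, can be read to include time within the 5 Gauss line in the scan. On that reading those 30 minutes are covered, so they are not counted here. What remains is programming and transfer time on either side. The documents give no length for it, so no duration can be calculated.

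3. **Therapy-off period against required monitoring.**

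| Interval | Sensing and tachytherapy | Stated ECG, oximetry or attendance duty |
|---|---|---|
| Activation to scan | Off (6.5.1.1) | None stated; set-up is described after activation |
| Scan | Off | Required (6.5.2.1, 3.7, Tables 1, 2, 5) |
| Scan end to disabling outside Zone 4 | Off (6.5.2.2) | None stated |
| After disabling | On | Not needed for this purpose |

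4. **Count of monitoring duties.** Six places set an ECG, oximetry or attendance duty for the study scan: Tables 1, 2 and 5, and sections 3.7, 6.5.1.1 and 6.5.2.1. All six refer to the scan; none runs until the Settings are disabled. In 6.5.1.1 the tie lies in the stated purpose of the electrodes and in the recording instructions; the instruction to set up has no time limit of its own.

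5. **Count of disabling instructions.** Five places list disabling for the study scan: Tables 1 and 5, and sections 3.7, 6.5.1.1 and 6.5.2.2. All five put it after a scan. A scan stopped early is arguably covered by 6.5.2.2, although the paragraph on subjects who cannot tolerate the scan does not mention disabling. A scan never started is covered by none of the five, and Table 7 does not fill that hole.

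6. **What limits the intervals.** There are three limits: the expectation that pre-scan, scan and post-scan procedures occur on one day (Tables 1 and 5); the order of steps in 6.5.2.2, where interrogation and disabling precede lead measurements; and, only for susceptible subjects in asynchronous mode, the instruction in 6.5.1.1 to keep asynchronous pacing short. None is a maximum time.

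7. **Who is exposed.** Enrollment requires the MRI Settings to be programmed (4.2.1, 4.6.2), so all enrolled subjects, up to 165, have therapy off for a time. This counts subjects with therapy off, not subjects left unmonitored.

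**The case against.** The strongest reply is that the CIP delegates scan conduct. Section 6.5.2.1 sends sites to the MRI systems manual for precautions, and Appendix E is kept under separate cover. Either may already extend monitoring. This stands, and it confines the point to the CIP text.

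Second, the subject is not simply unprotected. ACLS arrangements must exist without a time limit, disabling is among the first steps after bore exit, an electrophysiologist or device specialist confirms the pre-scan checks, and subjects are told to report symptoms straight after the scanner. This also stands, and it suggests the intervals are short. But arrangements are neither monitoring nor attendance, and a patient in ventricular fibrillation cannot report symptoms. The person at the programmer may be a sponsor field engineer (6.11), whom the CIP does not require to be one of the named monitors.

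Third, the pre-scan gap rests on paragraph order. This is correct: nothing tells sites to delay monitoring until after activation, and nothing tells them to remove it at scan end. The post-scan gap does not depend on that inference.

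Some stronger readings are tempting but unsupported. A reader might infer from 4.4.3 that the CIP permits late reprogramming; recording delays, if any, as data does not permit them, and 6.5.2.2 says the Settings must be disabled. A reader might take the same-day expectation as the only limit on the intervals; step 6 of the working shows two more. A reader might also treat the roughly 30 non-scanning minutes near the magnet as unmonitored; 8.1.6 allows the opposite reading.

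**Conclusion.** The point holds as a gap in the CIP text. The stated monitoring and attendance duties are tied to the scan, before tachytherapy is restored, and no stated duty covers the time between activation and scan. Table 7 adds a separate omission: Settings can have been programmed with no scan completed, and the listed actions contain no instruction to restore therapy.

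The size cannot be given in minutes. The intervals are probably short and have no stated maximum. The conclusion assumes that a duty expressed for the scan does not extend to the programmer location outside Zone 4. Even if the scan is taken to include the whole magnet-room stay, activation to entry and exit to disabling remain.

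A reader might conclude that subjects are in fact left unmonitored, or that the safety result is compromised. The documents support neither: the manual and Appendix E are not available here, and nothing in this point touches the endpoints, alpha or sample size. It is a cheap improvement that the sponsor should make, with medium confidence because of the unseen documents.

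**What to change.** - **6.5.1.1:** have ECG and oximetry running before the MRI Settings are activated.
- **6.5.2.1:** continue ECG, oximetry and attendance by the personnel already named there until the Settings are confirmed disabled and tachytherapy is confirmed on.
- **6.5.2.2 and Table 7:** whenever the Settings were programmed, require them to be disabled and therapy confirmed on before the subject leaves, including when the scan is not started or is stopped early.
- If the MRI manual or Appendix E already says this, cite it in 6.5.2.1 instead.

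Optional: matching words in 3.7 and Tables 1 and 5, and activation and deactivation times on the CRF to support the 4.4.3 summary of reprogramming delays.

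The cost is a few sentences and slightly longer attendance. The equipment and staff are already required at the visit.
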